16.2.2.1. Analysis of the Primary Endpoint

Counts and change from Baseline in counts for each of the lymphocyte subsets will be descriptively summarized at each applicable visit. Furthermore, the primary endpoints will be summarized in various ALC subgroups to evaluate the nature of change in each subset in relation to the change in ALC. Additionally, a mixed model for repeated measures (MMRM) will be used, which will be fit with the change from Baseline for each of the lymphocyte subsets as the dependent variable and will include ALC subgroups, visit, corresponding Baseline counts, age, gender, and ALC groups-by-visit interaction as fixed effects to estimate the difference between ALC subgroups. Point estimates and 2-sided 90% confidence intervals (CIs) will be derived from the model. Appropriate transformation may be performed based on the distribution of data.

[figure not shown]
ALC subgroups of interest include (1) subjects who have all ALC values \geq LLN up to Week 48, (2) subjects who have at least 1 ALC value $<$ LLN over 48 weeks, and (3) subjects who have at least 2 ALC values $<$ LLN over 48 weeks. Additional subgroups will be further defined in the Statistical Analysis Plan.

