16.7. Sample Size Considerations

The sample size for this study is not based on formal hypothesis testing but on the precision of the estimation of the primary endpoints and the ratios between various ALC subgroups.

For example, the Phase 2 and 3 controlled and uncontrolled efficacy and safety studies in MS, based on data available as of May 2014 from 2470 subjects with at least 1 post-Baseline value from the interim analysis of the Integrated Summary of Safety of Tecfidera, showed that 76% of subjects had all ALC values \geq LLN and 24% had at least 1 ALC value $<$ LLN up to Week 48.

Assuming the same proportion of subjects in this study will have 1 or more ALC values $<$ LLN, it is expected that approximately 137 subjects will have all ALC values \geq LLN and approximately 43 subjects will have at least 1 ALC value $<$ LLN at Week 48, based on a total of 180 evaluable subjects at Week 48. With this sample size, the 90% CIs for the ratio of the 2 subgroups for the change from Baseline at Week 48 in lymphocyte subsets are illustrated below using the scenario of a true ratio of 0.8 (20% decrease) and 0.7 (30% decrease), respectively. When assessing lymphocyte subsets between subjects with at least 2 ALC values $<$ LLN up to the first 48 weeks of treatment versus subjects who have all ALC values \geq LLN throughout the study, the 90% CIs of the ratio would be wider, as historical data suggest that 16% of the patients treated with Tecfidera may have 2 or more ALC values $<$ LLN during the first 48 weeks of treatment.

To allow for a 10% discontinuation rate, a total of 200 subjects are planned for enrollment.

CONFIDENTIAL

The information contained herein may not be used, disclosed, or published without the written consent of
Biogen MA Inc.

Table 6: Sample Size Calculations

Primary Endpoints	SD ¹	Ratio	90% CI for the Ratio Based on N = 180	
			Subjects With At Least 1 ALC <LLN ² vs. Subjects With All ALC ≥LLN ²	Subjects With At Least 2 ALC <LLN ² vs. Subjects With All ALC ≥LLN ²
CD4 T cell count	0.32	0.8	0.73, 0.88	0.71, 0.90
		0.7	0.63, 0.77	0.63, 0.78
CD8 T cell count	0.35	0.8	0.72, 0.89	0.71, 0.91
		0.7	0.63, 0.78	0.62, 0.79
CD56 ^{bright} NK cell count	0.57	0.8	0.68, 0.95	0.65, 0.98
		0.7	0.59, 0.83	0.57, 0.86
T _{reg} count	0.95	0.8	0.60, 1.07	0.57, 1.12
		0.7	0.52, 0.93	0.50, 0.98

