4 SAMPLE SIZE JUSTIFICATION

The sample size for this study is not based on formal hypothesis testing but on the precision of the estimation of the primary endpoints and the ratios between various ALC subgroups.

For example, the Phase 2 and 3 controlled and uncontrolled efficacy and safety studies in MS, based on data available as of May 2014 from 2470 subjects with at least 1 post-Baseline value from the interim analysis of the Integrated Summary of Safety of Tecfidera, showed that 76% of subjects had all ALC values \geq LLN and 24% had at least 1 ALC value $<$ LLN up to Week 48. Assuming the same proportion of subjects in this study will have 1 or more ALC values $<$ LLN, it is expected that approximately 137 subjects will have all ALC values \geq LLN and approximately 43 subjects will have at least 1 ALC value $<$ LLN at Week 48, based on a total of 180 evaluable subjects at Week 48. With this sample size, the 90% CIs for the ratio of the 2 subgroups for the change from Baseline at Week 48 in lymphocyte subsets are illustrated below using the scenario of a true ratio of 0.8 (20% decrease) and 0.7 (30% decrease), respectively. When assessing lymphocyte subsets between subjects with at least 2 ALC values $<$ LLN up to the first 48 weeks of treatment versus subjects who have all ALC values \geq LLN throughout the study, the 90% CIs of the ratio would be wider, as historical data suggest that 16% of the patients treated with Tecfidera may have 2 or more ALC values $<$ LLN during the first 48 weeks of treatment.

To allow for a 10% discontinuation rate, a total of 200 subjects are planned for enrollment.

Table 3: Sample Size Calculations

Primary Endpoints	SD ^{a)}	Ratio	90% CI for the Ratio Based on N = 180	
			Subjects With At Least 1 ALC $<$ LLN ^{b)} vs. Subjects With All ALC \geq LLN ^{b)}	Subjects With At Least 2 ALC $<$ LLN ^{b)} vs. Subjects With All ALC \geq LLN ^{b)}
	0.32	0.8	0.73, 0.88	0.71, 0.90

CONFIDENTIAL

The information contained herein may not be used, disclosed, or published without the written consent of Biogen Idec MA Inc.

biogen idec	Protocol 109MS310 An Open-Label Study to Assess the Effects of BG00012 on Lymphocyte Subsets in Subjects With RRMS	Final Version 1.0
--------------------	---	--------------------------

Primary Endpoints	SD^{a)}	Ratio	90% CI for the Ratio Based on N = 180	

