			Subjects With At Least 1 ALC <LLN^{b)} vs. Subjects With All ALC ≥LLN^{b)}	Subjects With At Least 2 ALC <LLN^{b)} vs. Subjects With All ALC ≥LLN^{b)}
CD4 T cell count		0.7	0.63, 0.77	0.63, 0.78
CD8 T cell count	0.35	0.8	0.72, 0.89	0.71, 0.91
		0.7	0.63, 0.78	0.62, 0.79
CD56 ^{bright} NK cell count	0.57	0.8	0.68, 0.95	0.65, 0.98
		0.7	0.59, 0.83	0.57, 0.86
T _{reg} count	0.95	0.8	0.60, 1.07	0.57, 1.12
		0.7	0.52, 0.93	0.50, 0.98

ALC = absolute lymphocyte count; CD = cluster of differentiation; CI = confidence interval; LLN = lower limit of normal; NK = natural killer; SD = standard deviation; T_{reg} = T regulatory; vs. = versus.

^{a)} Common standard deviation for the log-transformed change from Baseline.

^{b)} Up to Week 48.

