- 2) $0.5 \times 10^9/L \leq ALC < 0.8 \times 10^9/L$ for ≥ 6 months (excluding $< 0.5 \times 10^9/L$ for ≥ 6 months);
- 3) $<$ LLN any time (excluding $< 0.8 \times 10^9/L$ for ≥ 6 months);
- 4) ALC always \geq LLN.

Summary of actual value, change and percent change from baseline in count and percent for each lymphocyte subset will be presented by the ALC subgroups defined above.

The following subgroups analyses based on ALC during the first 48 weeks will be performed:

- 1) At least 2 ALC values $<$ LLN in the first 48 weeks;
- 2) Always \geq LLN or with one ALC $<$ LLN in the first 48 weeks

Additionally subgroups analyses based on baseline ALC quartiles will also be explored. The same descriptive summary on these subgroups will be applied to the count and percent for the TBNK lymphocyte subsets and may be applied to other subsets. Additional subgroups of interest may also be explored.

The correlation between TBNK actual value and ALC will be summarized by visit and also presented as plots.

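### SAP 5.3.1 sets subjects with at least two low ALC values beside a comparator that includes once-low subjects, whereas the sizing tables in both documents compare them with never-low subjects

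*SAP*

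**What the plan says.** Protocol 16.2.2.1 lists three ALC subgroups. They include "1) subjects who have all ALC values \geq LLN up to Week 48" and "3) subjects who have at least 2 ALC values $<$ LLN over 48 weeks"; the remaining one is subjects with at least one low value.

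Protocol 16.7 describes the second sized comparison as subjects with at least two low values "versus subjects who have all ALC values \geq LLN throughout the study, the 90% CIs of the ratio would be wider". SAP section 4 repeats this ("up to the first 48 weeks of treatment versus subjects who have all ALC values" at or above LLN). The right-hand interval column of protocol Table 6 and SAP Table 3 is headed the same way, with a footnote that limits both groups to the period up to Week 48.

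SAP 5.3.1 then sets out these analyses:

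- The mixed model for repeated measures (MMRM) compares at least one low value with all values at or above LLN up to Week 48.
- A separate 48-week split has two groups. The first is "At least 2 ALC values $<$ LLN in the first 48 weeks". The second is subjects always at or above "LLN or with one ALC $<$ LLN in the first 48 weeks".
- For that split, "The same descriptive summary on these subgroups will be applied to the count and percent for the TBNK lymphocyte subsets", and other subsets are optional.

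The readable text of SAP 5.7 records one change of method, to the clinical assessment population. It does not mention this comparator.

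**The concern.** The two groups in the 48-week split are complementary, so the second is the only comparator that the split offers. It mixes never-low subjects with subjects who had one low value. Those once-low subjects count as affected in the at-least-one split and as comparator in this one.

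The SAP says the subgroups are there to relate subset change to ALC change. If once-low subjects lose some cells, placing them in the comparator brings the two columns closer together. A reader who takes the table as the counterpart of the right-hand column of Table 3 would be looking at a different comparison, with no note that it had changed.

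**Working it through.** **Inputs (protocol 16.7, repeated in SAP section 4).** Evaluable N = 180; 76% with no low value, 24% with at least one, 16% with at least two; illustrated ratios 0.8 and 0.7; log-scale SD 0.32 for CD4; 90% intervals.

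**Reproducing the plan's figures.** The group sizes reproduce: 180 × 0.76 = 136.8 (137) and 180 × 0.24 = 43.2 (43). For at least two, 180 × 0.16 = 28.8 (29).

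The printed intervals do not reproduce exactly at N = 180. For CD4 at ratio 0.8 with 29 against 137:

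0.8 × exp(±1.645 × 0.32 × √(1/29 + 1/137)) = 0.718 to 0.891, printed as 0.71 to 0.90.

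Across the right-hand column, 5 of 16 limits match, with a largest gap of 0.019. Using the SAP 5.3.1 comparator (29 against 151) also matches 5 of 16. The numbers therefore cannot show which comparator was used; the column headings and sizing text do. The interval discrepancy is a separate matter and does not affect this point.

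**Composition of the SAP comparator.** Exactly one low value: 24% − 16% = 8%, or 180 × 0.08 = 14.4 (14). The comparator is 137 + 14 = 151. The once-low share is f = 14/151 = 9.3% from rounded counts, or 8/84 = 9.5% from the rates.

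**Dilution.** Let r2 be the ratio of the at-least-two group to never-low subjects, and r1 the ratio of once-low to never-low subjects. The log ratio read across the SAP's two columns is

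ln(r2) − f × ln(r1).

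The documents give no r1. Assuming it lies between 1 (no effect) and r2 (as affected as the at-least-two group), with f = 8/84:

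| Once-low ratio r1 (assumed) | True 0.80 appears as | True 0.70 appears as |
|---|---|---|
| 1.0 | 0.800 (0% log attenuation) | 0.700 (0%) |
| 0.9 | 0.808 (4.5%) | 0.707 (2.8%) |
| 0.8 | 0.817 (9.5%) | 0.715 (6.0%) |
| 0.7 | outside the assumed range | 0.724 (9.5%) |

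With f = 14/151 the upper end is 9.3%, and 0.817 and 0.724 are unchanged to three decimals. The same weight f applies to a difference in arithmetic mean change. A difference in medians would not follow this formula.

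**Precision.** √(1/29 + 1/137) = 0.2044 and √(1/29 + 1/151) = 0.2027. Restoring the never-low comparator would widen an interval by 0.2044/0.2027 − 1, about 0.8%.

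**The case against.** The strongest reply is that SAP 5.3.1 plans no contrast here. The split has no named reference, ratio, interval or test. The at-least-two column reports that group's own values and changes, which do not depend on who is in the other column. The modelled comparison, at least one low against none, keeps a clean never-low group. Never-low subjects are also summarised in the at-least-one split and as an always-at-or-above-LLN group in the over-time classification. Cutting at two or more against one or fewer is an ordinary choice, and protocol 16.2.2.1 leaves further subgroups to the SAP.

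Most of this stands, and it limits the point. What remains is narrower. No planned split puts at-least-two beside never-low subjects over 48 weeks, and the over-time group states no 48-week limit. Permission to add subgroups does not explain why Table 3 still illustrates a comparator that 5.3.1 does not use for this group.

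A reader might go further and infer lost power, or a lower chance that a 90% interval excludes 1, especially for CD56bright NK cells and Treg, where the SDs are largest. The documents do not support that. The SAP computes no such interval for this split, and the sample size rests on precision, not testing. Appendix 1 lists those two subsets outside the TBNK panel, so the split is only optional for them. Of the four sized endpoints, it is firm for CD4 and CD8 only.

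**Conclusion.** The mismatch is real, both between the SAP and the protocol and between SAP section 4 and SAP 5.3.1. Its effect is limited to the difference a reader takes between two descriptive columns. That difference is attenuated by 0% to about 9% on the log scale. Even the upper end, 0.80 appearing as 0.817, is small beside the printed CD4 interval of 0.71 to 0.90.

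The range rests on the historical rates carrying over to this study and on once-low subjects being no more affected than the at-least-two group. It would be tempting to treat the upper end as the plan's own expectation, because Table 6 uses the same ratios in both columns. Those ratios are illustrative scenarios and say nothing about once-low subjects separately. Nor does the split understate the subset changes reported for the at-least-two group itself. This is a minor alignment point.

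**What to change.** In SAP 5.3.1, replace the two-group 48-week split with three mutually exclusive groups shown side by side: all ALC values at or above LLN, exactly one below, and at least two below, each up to Week 48. Name the first as the comparator for the third, as in SAP section 4.

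This takes one wording change and one extra table column, with no new data. The once-low column will be imprecise at about 14 subjects, and the comparator falls from about 151 to 137. If the sponsor prefers the present split, SAP 5.7 should record the change of comparator and Table 3 should be brought into line with it.

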5.3.2 Analysis of the Secondary Endpoints

The secondary endpoints are the changes from baseline in Ig isotypes (including IgA, IgM, IgG and IgG subclasses) and ALCs for up to 48 weeks. The actual values, change and percent change from baseline for Ig isotypes and ALCs at each applicable visit will be descriptively summarized. Graphical display of mean (+/- SE) of actual values and percent change from baseline over time in Ig isotypes will be presented as well. Individual patient's Ig isotypes will also be listed.

In addition, MMRM analysis will be conducted for each Ig isotype and for ALC with the change from baseline up to Week 96 as the dependent variable. The model will include visit, corresponding baseline value, age, and gender as fixed effects and an unstructured variance-covariance matrix structure. LS mean, standard error and 95% CIs will be reported for each visit.

CONFIDENTIAL

The information contained herein may not be used, disclosed, or published without the written consent of Biogen Idec MA Inc.

5.3.3 Lymphocyte analysis during lymphocyte follow-up period

Subjects who temporarily withhold, or permanently discontinue study treatment for any reason and have a lymphocyte count <LLN will continue protocol-required visits and assessments and will also be followed up every 4 weeks for 24 weeks, then every 12 weeks (unless clinically indicated more often or at the Investigator's discretion) until the lymphocyte count is \geq LLN or for up to 48 weeks following drug discontinuation, whichever occurs sooner.

In general, the lymphocyte follow-up analysis will include subjects who have at least one ALC < LLN during the treatment period and have at least one ALC value during the lymphocyte follow-up period. The lymphocyte follow-up period is defined as the time starting from the date of temporary dose interruption or study drug discontinuation. The start date of the lymphocyte follow-up period is defined as the start date of temporary dose interruption or the treatment end date. The last observed value collected on or prior to the date of temporary dose interruption or study drug discontinuation will be the reference point (lymphocyte follow-up baseline). Data that are collected during the lymphocyte follow-up period will be assigned to an appropriate visit by using the mid-point of the two visits windowing scheme. Visits will be mapped every 4 weeks for 24 weeks and then every 12 weeks afterward. The detailed windowing rule is available in [Appendix 2](#). Patients who have any post lymphocyte follow-up baseline values will be included in the analysis. ALCs collected during the lymphocyte follow-up period will be analyzed. The lymphocyte subsets and Ig isotypes observed obvious decline over time in the treatment period will also be explored.

The by-visit summary of actual value, change and percent change from the lymphocyte follow-up baseline in ALC during the lymphocyte follow-up period will be presented. The by-visit summary of actual value, change and percent change from the study baseline in ALC during the whole study period will also be presented. In addition, graphical display of median (Q1/Q3) of actual value in ALC in the whole study period will be presented; graphical display of median (Q1/Q3) of percent change from study baseline and lymphocyte follow-up baseline will be presented. The same analyses will be applied to selected lymphocyte subsets and Ig isotypes of interest.

The concomitant medication, AEs, hematology, vital signs and physical examination data collected during the lymphocyte follow-up visits will be discussed in [Section 5.4.6](#).

Additional analyses exploring lymphocyte subsets and ALCs collected during the lymphocyte follow-up period may be conducted.

CONFIDENTIAL

The information contained herein may not be used, disclosed, or published without the written consent of Biogen Idec MA Inc.

	Protocol 109MS310 An Open-Label Study to Assess the Effects of BG00012 on Lymphocyte Subsets in Subjects With RRMS	Final Version 1.0
---	---	--------------------------

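### The lymphocyte follow-up analysis pools subjects who were already at or above LLN when drug was stopped with those who were below it; the planned output should be split by ALC at stop

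*SAP*

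**What the plan says.** SAP 5.3.3 opens with who is followed: "Subjects who temporarily withhold, or permanently discontinue study treatment for any reason and have a lymphocyte count <LLN will continue protocol-required visits and assessments". They have extra counts until ALC is back at LLN or 48 weeks have passed. LLN is 0.91 x 10^9/L (SAP 5.3.1).

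The analysis set is defined by other conditions: "the lymphocyte follow-up analysis will include subjects who have at least one ALC < LLN during the treatment period", and who also "have at least one ALC value during the lymphocyte follow-up period". Neither refers to ALC at the time drug is interrupted or stopped. The reference value (lymphocyte follow-up baseline) is the last value on or before that date, whatever its level. Further down, the section gives a second, looser rule: "Patients who have any post lymphocyte follow-up baseline values will be included in the analysis".

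The period is defined by date, with no stated end: "The lymphocyte follow-up period is defined as the time starting from the date of temporary dose interruption or study drug discontinuation". The next sentence puts it slightly differently: "The start date of the lymphocyte follow-up period is defined as the start date of temporary dose interruption or the treatment end date".

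The planned output is by-visit ALC, with change and percent change from both the follow-up baseline and the study baseline, plus median (Q1/Q3) plots. The same analyses apply to selected subsets and Ig isotypes. No split by ALC at stop is planned; the section says only that additional analyses may be done.

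**The concern.** The follow-up visits exist to see what happens to low counts once drug is withheld or stopped. The analysis set is wider than that group. A subject with one low ALC at Week 8 and normal values afterwards qualifies, with a follow-up baseline already ≥LLN.

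Two effects follow. The plotted ALC level is lifted by subjects who were not lymphopenic at the stop. If those subjects rise less than the low ones, the median change from follow-up baseline also shrinks. Subjects ≥LLN at stop are not scheduled for the four-weekly visits, so both effects should be strongest in the four-week window, and the mix of subjects changes between windows.

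Protocol 5.3.2 links PML to prolonged moderate to severe lymphopenia, so readers will look to this output to judge whether low counts come back off drug.

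**Working it through.** **1. Can subjects ≥LLN at stop enter?** Yes. SAP Table 1 schedules a Final Follow-Up Visit with a CBC 4 weeks (±5 days) after the last dose, and its first footnote makes this the standard visit for subjects not <LLN. The follow-up window table in SAP Appendix 2 assigns Day 2 to Day 42 to the four-week visit (target Day 29); Day 29 ± 5 is Day 24 to Day 34, inside it. Early discontinuers also have a CBC at the Discontinuation Visit (SAP Table 2). Subjects ≥LLN who interrupt for another reason keep their routine CBCs, so a few could reach later windows.

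**2. The plan's own figures (SAP 4).** 0.76 x 180 = 136.8 (stated: about 137); 0.24 x 180 = 43.2 (about 43); 180/0.90 = 200. All reproduce. None concerns the follow-up analysis.

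The SAP gives 24% with at least one ALC <LLN by Week 48, and "historical data suggest that 16% of the patients treated with Tecfidera may have 2 or more ALC values" below LLN. If both come from the same data, (24 - 16)/24 = 1/3 of ever-low subjects had exactly one low value by then (0.08 x 180 = 14.4 of 43.2). This is not the share ≥LLN at stop, because the single low value may be the last one. In simulations of the model in step 4, it fell at Week 48 in 37-92% of these subjects.

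**3. Effect for an assumed share.** Let f be the share ≥LLN at stop, and d their rise divided by the rise in low subjects. The mean change retained is (1 - f) + f x d. With d = 0 this is 90%, 80%, 67% and 50% for f = 0.10, 0.20, 1/3 and 0.50. With d = 1 it is 100%.

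The plan plots medians, so these were simulated. Assumed: low at stop, ALC about 0.70 (SD 0.12) and a 25% rise; ≥LLN at stop, ALC about 1.15 (SD 0.20) and a rise of 0, 10 or 25%; SD of percent change 25. Each cell gives median percent change / median post-stop ALC (x 10^9/L).

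| f | rise 0% | rise 10% | rise 25% |
|---|---|---|---|
| 0 | 25.0 / 0.85 | 25.0 / 0.85 | 25.0 / 0.85 |
| 0.10 | 22.8 / 0.87 | 23.7 / 0.88 | 25.0 / 0.88 |
| 0.20 | 20.5 / 0.90 | 22.1 / 0.91 | 25.0 / 0.92 |
| 1/3 | 17.1 / 0.93 | 20.0 / 0.95 | 25.1 / 0.98 |
| 0.50 | 12.5 / 0.99 | 17.6 / 1.03 | 25.1 / 1.10 |

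The ALC level is lifted in every column. The change is diluted only where the ≥LLN group rises less.

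**4. What f might be for Week 96 completers.** Assumed model: log-normal baseline ALC with an entry value above 0.91; mean fall of 30% by Week 48 (Protocol 5.3.2), linear or early, then a plateau; random slopes; visit noise SD 0.10-0.20 on the log scale; fitted approximately to 24% and 16% (achieved about 24-26% and 12-17%). Across fits:
- ≥LLN at Week 96 among subjects ever <LLN on treatment: 25-45%
- ≥LLN four weeks later with no effect of stopping: 27-50%
- median follow-up baseline ALC: 0.78-0.88 in the ever-low set, 0.71-0.79 in those <LLN at stop

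**5. What selecting on the last value does.** Same model, no effect of stopping, median percent change at four weeks:
- SAP ever-low set: 0.4-1.4%
- follow-up baseline <LLN: 2.7-12.7%
- last two on-treatment ALCs both <LLN: 1.4-7.4%

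**The case against.** The strongest counter-argument is that the SAP's set is close to unbiased for change when stopping has no effect (step 5), whereas restricting it to subjects <LLN at stop selects on the same value used as the baseline and so produces an apparent rise. That stands. A reader might infer that the set should simply be replaced by subjects low at stop; the check does not support this, because the swap exchanges one distortion for another.

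Three further objections also stand.
- **Completers.** A reader might infer that every ever-low completer enters. Only the phrase about the treatment end date points that way. The sentence before it speaks of interruption or discontinuation, and so does the opening paragraph. The lymphocyte follow-up footnote of SAP Table 2 omits completers, while the matching footnote of Protocol Table 2 includes them. Subjects <LLN at Week 96 are followed outside the study after the Final Follow-Up Visit. The SAP leaves the question open, and every figure in step 4 depends on it.
- **Room to rise.** A reader might infer that subjects ≥LLN at stop have nothing to regain. Mean ALC falls about 30% on drug, and in the simulations ever-low subjects who were ≥LLN at stop had fallen to about 55-69% of their own baseline. They may rise too.
- **Stakes.** The stated primary and secondary endpoints cover the first 48 weeks, and this section is descriptive. It opens its inclusion rule with a general qualifier, shows quartiles and change from study baseline, and hematology is listed by subject.

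None of this removes the mixing of lymphopenic and normal subjects in the ALC level curves, or the conflict between the two inclusion sentences.

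**Conclusion.** The point holds in a limited form. Entry to the follow-up analysis depends on any low ALC during treatment, and under the looser sentence not even on that, while the follow-up itself is for subjects low at the stop. Absolute ALC summaries are therefore biased upward as a description of lymphopenic subjects. Change from follow-up baseline is biased toward zero only if subjects ≥LLN at stop rise less.

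The size cannot be derived from the documents. About 25-50% is an assumption-driven range for Week 96 completers alone; for early stoppers and interrupters, the group that the section names, no share is established. The one-third figure in step 2 should not be quoted as the share ≥LLN at stop.

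A reader might also infer that these subjects would be reported as recovered. The SAP plans no recovery category, recovery proportion or time to recovery in this section, so the issue is confined to the by-visit summaries and median plots. It is a cheap improvement to a descriptive analysis, not an error that threatens the study's endpoints.

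**What to change.** In SAP 5.3.3:
- Keep the set of subjects ever <LLN on treatment with a post-stop ALC, but present the by-visit ALC, change and percent-change tables and the median plots separately by lymphocyte follow-up baseline ALC (<LLN versus ≥LLN). Do the same for the selected subsets and Ig isotypes.
- Add a sensitivity table for subjects whose last two on-treatment ALCs were both <LLN.
- State that change from follow-up baseline in the <LLN stratum includes regression to the mean (illustratively a 3-13% median rise with no effect of stopping, and 1-7% in the two-value set), and show change from study baseline beside it.
- Reconcile the two inclusion sentences, and state whether Week 96 completers are included.

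The cost is SAP wording and a derived flag for ALC at stop; no new data are needed. The downside is smaller strata, with regression to the mean within them. The split does not remove the change of case mix between windows: completers still <LLN at Week 96 would contribute only to the four-week window, and scheduled follow-up ends once ALC reaches LLN.
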